5.1 Overall design (including assumptions, type, etc.)

This study hypothesized that selmetinib hydroxyl sulphate capsules are effective in neurofibromatosis type I, including improving efficacy after tumor resection, delaying progression, reducing recurrence, and improving function. The prospective, single-arm, phase-study study protocol was designed to estimate progression-free survival (PFS) in more than 50% of NF 1 patients at 24 months, objective response rate (ORR) of 40%, and duration of tumor response (DOR) of 12 months.

5.2 Study design process

5.2.1 Study the specific implementation process

This study started from the recruitment of subjects, with clinical diagnosis, definite diagnosis by pathological biopsy, primary screening according to inclusion criteria and exclusion criteria, and signed informed consent before enrollment. After evaluation as indication for surgical resection and surgical treatment, selmetinib hydrosulphate capsules. PFS, ORR and DOR were assessed after 6 cycles of oral selhydrosulphate capsules (20–50mg bid).

Demographic data	✓										
medical history	✓				✓			✓	✓	✓	✓
ECOG grade	✓	✓	✓	✓	✓	✓	✓	✓	✓	✓	✓
check-up	✓	✓	✓	✓	✓	✓	✓	✓	✓	✓	✓
vital sign	✓	✓	✓	✓	✓	✓	✓	✓	✓	✓	✓
electrocardiogram	✓				✓			✓	✓	✓	✓
routine blood test	✓		✓	✓	✓	✓	✓	✓	✓	✓	✓
Blood biochemical	✓		✓	✓	✓	✓	✓	✓	✓	✓	✓
Liver, kidney, and cardiac function	✓		✓	✓	✓	✓	✓	✓	✓	✓	✓
coagulation function	✓		✓	✓	✓	✓	✓	✓	✓	✓	✓
Heart ultrasound	✓				✓			✓	✓	✓	✓
Pathological biopsy	✓										
Infectious disease examination (hepatitis B, hepatitis C, HIV, syphilis)	✓										
Imaging examination	✓				✓			✓	✓	✓	✓
complication And adverse event assessment			✓	✓	✓	✓	✓	✓	✓	✓	✓

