Clinical study protocol

Project Name: A prospective, single-arm, phase II clinical study of selmetinib hydrosulphate capsules for treating postoperative patients with neurofibromatosis type I

Sponsor: Sun Yat-sen Memorial Hospital of Sun Yat-sen University

Version number: V2.0

Version date: 2024.04.17

Project leader: [name]

Scheme signature confirmation:

Compliance Statement

In accordance with the provisions of the Good Clinical Practice for Drug Clinical Trials and the Administrative Measures for Clinical Studies initiated by Medical Institutions (Trial) and the Declaration of Helsinki, we promise to carry out this study according to this protocol. The participants must be trained to conduct the study after the written approval of the Ethics Committee and the written informed consent of the subjects, and the protocol revision shall be re-approved again.

1. Protocol abstract (title, brief description of study, study object, outcome measures, study intervention*, Sample size, etc., in 300–500 words)

This study focuses on patients with neurofibromatosis type I, who lack effective medical therapy and has a high recurrence rate after surgical resection. For patients with small solid tumors, limited space occupying, and not invading the brain, spine and other important organs, surgical treatment is the main treatment means. As a MEK inhibitor, by selectively binding the mitogen-activated protein kinase (MEK) 1 / 2 protein, it can block the mitogen-activated protein kinase / extracellular signal-regulated kinase signaling pathway that regulates key cellular responses, and can induce tumor shrinkage and reduce postoperative recurrence. The purpose of this study is to treat hydrosulphate for patients with surgical indications, to observe the efficacy of drug treatment, consolidate the postoperative efficacy and reduce the recurrence rate. In this study, progression-free survival (PFS) after drug treatment was used as the main study outcome measure, duration of remission (DOR) and objective response rate (ORR) as secondary outcome measures to explore the use of selmetinib sulphate for tumor control efficacy, reduction of recurrence rate, and stability of efficacy in patients with neurofibromatosis type I.

2. Introduction (references to be noted in the introduction)

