4.1 Inclusion criteria

- (1) Age ≥ 18 years old
- (2) According to the updated NF 1 diagnostic criteria of the National Institutes of Health (NIH) in 2021,
 - ① 6 or more CALMs: $d > 5$ mm before puberty or $d > 15$ mm after puberty;

② 2 or more neurofibromas of any type or 1 plexiform neurofibroma;

③ Plaques in the axillary or inguinal area;

④ Optic glioma (OPG);

⑤ Slit lamp examination of two or more Lisch nodules, or optical coherence tomography (OCT) / imaging of two or more near infrared (NIR) choroid abnormalities;

⑥ Characteristic bone lesions, such as sphenoid dysplasia and anterolateral curvature of the tibia;

⑦ Pathogenic heterozygous NF 1 variants with allelic variant scores of 50% in normal tissues (such as leukocytes);

Patients with no parental history and fulfilling 2 or more clinical characteristics could be diagnosed with NF 1

Parents with a history of 1 or more clinical features can be diagnosed with NF 1

(3) Before enrollment, a head and neck surgeon performed a pathological biopsy of the solid tumor to clarify the pathological diagnosis and exclude the malignant peripheral schwannoma (MPNST)

(4) At least one measurable tumor lesion according to the efficacy evaluation criteria of solid tumors RECIST 1.1

(5) The tumor did not invade the brain, spine and other important organs, and there are indications for surgical resection and surgical treatment

(6) The performance status of the Eastern Cooperative Oncology Group (Eastern Cooperative Oncology Group, ECOG) was 0-1

(7) Blood routine: white blood cell count (WBC) 3.010^9 / L; Absolute neutrophil count (ANC) 1.510^9 / L; Platelet (PLT) 10010^9 / L; hemoglobin level (HGB) 9.0 g/dL (no corresponding supportive care, such as transfusion and increased leukocytes within 7 days).

(8) Liver function: 2.5 times aspartate aminotransferase (AST) and alanine aminotransferase (ALT); albumin (ALB) 30 g / L.

(9) Renal function: serum creatinine 1.5 times ULN or creatinine clearance (CrCl) 50 mL/min (using the Cockcroft / Galt formula); urinary protein (UPRO) <(+ +), or 24-hour urinary protein <1.0 g.

(10) Cardiac function: blood creatine phosphokinase 200U / L, left ventricular ejection fraction (LVEF) 50%;

(11) Did not participate in other clinical trials within the previous 30 days;

(12) Patients who voluntarily participate in the project and sign the informed consent form.

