4.2 Exclusion criteria

(1) The patient had abnormal blood indexes, abnormal liver and kidney heart function, and cannot tolerate the clinical study process after multidisciplinary consultation and evaluation

(2) The patient has become malignant peripheral nerve schwannoma (MPNST) or has serious complications such as other malignant tumors and heart disease, or has been treated with anti-tumor therapy such as chemotherapy and radiotherapy

(3) The whole clinical study cannot be completed due to personal, social and economic reasons

(4) There are previously serious systemic system diseases and the disease cannot be cured or drug control

(5) Patients who are present in pregnancy

4.3 Lifestyle considerations (lifestyle related restrictions: smoking, drinking, exercise, diet, etc., and what measures will be taken if the subject needs drugs, treatments or surgery prohibited in the protocol)

After entering the clinical study, the subject needs a light diet, food, tobacco, alcohol, and no strenuous exercise. If the subject needs

the drug, treatment or surgery unrelated to the study, the investigator needs to evaluate whether the cause of the need for the drug, treatment and surgical treatment is the adverse event of the study, additional treatment due to accident or other reasons, consider the impact of the treatment on the course of the study, then advise the subject to receive conventional treatment after withdrawal and seal the subject data.

4.4 Screening failures (definition of screening failures and how to process screening failed subjects)

Screening failure refers to the recruitment of subjects who failed to meet the inclusion criteria or the exclusion criteria after multidisciplinary evaluation. The study will inform the results of the multidisciplinary consultation and give the current best treatment advice.

4.5 Recruitment and retention strategy (how to recruit subjects (location, method, expected number.....); How to retain subjects (multiple contact information, incentive); such as involving vulnerable groups: reason + safeguard measures; if having compensation or incentive measures: object, quantity, form, time, etc.)

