9.1 Case report form / electronic data records

Prior to the start of the study, the Redcap electronic database / EDC database was established based on the content of the paper version of the case report form.

9.2 Data management (data collection form, data storage carrier: electronic / paper, data integrity inspection, database establishment method, data management system, data quality detection method, definition of data lock library, etc.)

The original data should be uniformly recorded in the study medical records. According to the content of the study medical record, the case report form can be completed in the electronic database to ensure the integrity and accuracy of the information. In order to ensure the accuracy of the data, the researcher shall conduct self-examination no less than twice a year, regularly appoint personnel to the sub-center for project quality control, and accept the examination by the hospital and school management departments. If the data registered in the case report form / electronic database are inconsistent with the original records (study medical records), the investigator shall organize timely verification of the data, modify the wrong part according to the requirements of GCP regulations, and make corresponding explanations if necessary.

10. Ethics requirements

This study complied with the provisions of Good Clinical Practice and the Administration of Investigator-Initiated Clinical Studies (Trial) and the Declaration of Helsinki. This study will be conducted only before the ethical committee of the trial. In the course of the study process, the revised protocol must be resubmitted to the Ethics Committee for review, and the investigator must wait until the consent of the Ethics Committee before implementing the new protocol.

Each enrolled patient must sign an informed consent form. Copies of the informed consent form and contact information of the investigator and the ethics committee must be provided to the requested patients*. This study will collect the clinical data and personal information of the research subjects for scientific research, which will involve the privacy rights of the patients. The study participants and data analysts signed a confidentiality agreement not to disclose patient personal information and disease-related information to any individuals and institutions unrelated to the study. The collected patient data should be managed to prevent personal privacy leakage.

11. References

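### Section 5.2.1 lists the required biopsy and eligibility screening ahead of signed consent, so a candidate who fails screening could undergo study-required procedures before consenting

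*Protocol*

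**What the plan says.** Section 5.2.1 is the only place where the protocol sets out the steps from recruitment to treatment. It starts with recruitment and continues: "with clinical diagnosis, definite diagnosis by pathological biopsy, primary screening according to inclusion criteria and exclusion criteria, and signed informed consent before enrollment". The visit schedule in the same section ticks the biopsy and the infectious-disease tests once, in the first column. Heart ultrasound and imaging are ticked in that column and again later.

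Inclusion criterion (3) in section 4.1 makes the biopsy a condition of entry: "Before enrollment, a head and neck surgeon performed a pathological biopsy of the solid tumor to clarify the pathological diagnosis", with exclusion of MPNST as part of its purpose. Criterion (12), the last in the list, is consent itself: "Patients who voluntarily participate in the project and sign the informed consent form". It gives no timing relative to the other criteria.

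Section 4.4 defines the people who do not get through: "Screening failure refers to the recruitment of subjects who failed to meet the inclusion criteria or the exclusion criteria after multidisciplinary evaluation". It says they will be told the consultation result and given treatment advice. It does not mention consent.

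Section 10 (Ethics requirements) states the duty as follows: "Each enrolled patient must sign an informed consent form".

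The compliance statement at the front of the protocol commits to GCP and the Declaration of Helsinki and places conduct of the study "after the written approval of the Ethics Committee and the written informed consent of the subjects".

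**The concern.** A biopsy is invasive, and the infectious-disease panel includes HIV and syphilis. Where the protocol requires such procedures to decide eligibility, a reader expects consent to be signed before them. Section 5.2.1 names them first and consent last, and section 10 words the duty around people who have already passed screening. Between these two passages, nothing operational covers a candidate who is tested and then found ineligible.

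What is at stake is the protection of candidates, and whether the protocol agrees with its own commitment at the front. Site staff work from the operational sequence, so a general commitment elsewhere may not correct what they do.

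**Working it through.** No arithmetic applies. The check sets every statement on consent, biopsy and screening side by side and then follows candidates through them.

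| Place in the protocol | What it fixes | What it leaves open |
|---|---|---|
| Compliance statement | Study conduct follows ethics approval and written consent | Whether screening counts as conduct; biopsy is not mentioned |
| 4.1, criterion (3) | Biopsy must precede enrollment | Whether it precedes or follows consent |
| 4.1, criterion (12) | Signing is an entry criterion | When it is signed relative to the tests behind the other criteria |
| 4.4 | Who is a screening failure | Whether such a person has consented |
| 5.2.1, text | Consent comes before enrollment; biopsy and screening are named ahead of it | Any explicit rule that consent precedes them |
| 10 | Enrolled patients must sign | Candidates who are never enrolled |

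**Step 1: the order in 5.2.1.** The sentence opens with where the study starts and closes with enrollment, so the natural reading is chronological: recruitment, clinical diagnosis, biopsy, screening, consent, enrollment.

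**Step 2: is the biopsy required by the protocol?** Yes. Criterion (3) requires it before enrollment, and the schedule lists it. It also helps decide eligibility, because MPNST is ruled out by criterion (3) and again by exclusion criterion (2).

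**Step 3: three candidates followed through the text.**
- *Biopsy shows MPNST.* The candidate is recruited, diagnosed clinically and biopsied, then fails criterion (3). On the chronological reading this person never reaches the consent step. Section 10 does not reach them either, because they are not enrolled.
- *Fails on laboratory values or LVEF, criteria (7) to (10).* Blood tests or a heart ultrasound, and possibly the biopsy, could come before the consent step.
- *Eligible and enrolled.* Consent is signed before enrollment, so it is on file. On the chronological reading it is still later than the biopsy.

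**Step 4: the alternative reading.** Suppose the 5.2.1 sentence is only an unordered list of things needed before enrollment. The direct conflict with the compliance statement then disappears. The gap does not: no passage says that consent precedes the biopsy or any other screening test, and section 10 still speaks only to people who have been enrolled.

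**Step 5: does another passage close the gap?** Section 4.5 describes on-site registration and individual explanation at recruitment. That gives information but is not signed consent. The compliance statement is the broadest text. It conflicts with the chronological reading of 5.2.1 and is silent on screening under the other reading.

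**The case against.** The strongest reply has four parts.

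*The order is inferred.* The sentence in 5.2.1 is translated prose, its items joined by commas, and its only explicit timing is that consent comes before enrollment. This stands as a limit: the order is the natural reading, not a stated rule. It does not remove the point, because on either reading nothing places consent ahead of study-required tests.

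*Consent is covered elsewhere.* Criterion (12) makes signing part of eligibility, and both the compliance statement and section 10 invoke GCP. A reader might infer from section 10 that enrolled patients alone need to consent. The text does not say so. It states a duty for enrolled patients and is silent on others. That silence is what needs filling.

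*The biopsy may be routine.* Criterion (3) describes clarifying a diagnosis in patients with surgical indications, which fits ordinary work-up done under clinical consent. This is possible, and the protocol does not settle it. However, section 4.5 also recruits through posters, leaflets, lectures and online, so candidates need not arrive already biopsied.

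*The schedule proves little.* The column headings of the visit table cannot be read in the copy reviewed. The first column therefore shows that the tests belong to the earliest visit, not that they come before consent. This stands, and the conclusion does not rest on the table.

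**Conclusion.** The point holds in a limited form. Followed as written, 5.2.1 and section 10 allow a candidate who fails screening to have a biopsy or another study-required test before consenting, and this conflicts with the compliance statement. The conclusion rests on reading 5.2.1 chronologically and on the biopsy being, for at least some candidates, a procedure done for the study.

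Three stronger conclusions might be drawn, and the documents support none of them.
- That every screening failure has a biopsy without consent. A candidate can fail on age, ECOG status, laboratory values or pregnancy without being biopsied, and nothing says that everyone is biopsied first.
- That the number affected can be estimated. The protocol gives no screening-failure rate, and the 19 planned subjects all sign before enrollment.
- That baseline or screening data would be unusable. No passage says so. Section 4.4 concerns telling candidates their result and advising them, not using their data.

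The point concerns ethics and conduct. The sample size of 17, raised to 19 for dropout, and the one-sided 0.025 level do not depend on it. It should be corrected because the procedure is invasive, some tests are sensitive, and the correction is small.

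**What to change.** Three wording changes:

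1. In 5.2.1, move signed informed consent so that it follows recruitment and precedes any study-specific screening procedure.
2. In section 10, extend the requirement from enrolled patients to each candidate, to be met before any study-specific procedure.
3. State that a biopsy or test already done as routine care before consent may be used for eligibility without being repeated.

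These bring the operational text into line with the compliance statement. They add no procedure and alter no eligibility criterion; the same consent step simply happens earlier. The small downside is the time spent on consent discussions with some people who then fail screening. As a protocol revision, the change needs ethics committee approval under section 10 before it is used.

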5.3 Methods to reduce bias (e. g., randomization, blindness, matching method, etc.)

The end of this study was defined as the last subject who completed the last follow-up or was lost to follow-up or died

5.4 Definition of end of study (e. g. last subject completes last follow-up)

5.5 Statistical analysis

5.5.1 Sample size and basis for calculation

The estimated sample size was based on the objective response rate. The hypothesis of this study is that selmetinib sulphate can reduce the recurrence rate of patients after NF 1. The study parameters were set: $\alpha = 0.025$ (unilateral), Power=80%, and progression-free survival (PFS) in 20% of patients with NF 1 for 24 months. More than 50% of progression-free survival (PFS) in NF 1 patients. 17 cases were calculated using PASS 15.0 software, considering 10% shedding rate, 19 subjects should be included.

.5.52 Data analysis set (e. g. full analysis set, compliance protocol set, safety analysis set)

Statistical analysis will be performed using the SAS statistical software (V. 9.4, SAS Institute) Statistical analysis software for calculation, if no special instructions, the main indicators use one-sided test, control the first class error α is 0.025, the remaining indicators use two-sided test, one class error is $\alpha = 0.05$. To calculate confidence intervals, calculate two-sided 95% confidence intervals if not otherwise specified.

(1) Full analysis set (full analysis set, FAS): consisting of all subjects who received at least one drug / treatment and obtained efficacy assessment. This dataset was derived from all subjects after removing subjects in the least and reasonable way.

(2) Safety analysis set (safety analysis set, SS): a population treated at least once / once and having at least one safety evaluation data. In the safety analysis, all patients will be analyzed by the actual drug group.

(3) Compliance with the protocol set (per-protocol set, PPS): all concomitant medications that met the trial protocol and did not use the

impact effectiveness evaluation, good medication compliance (between 80% and 120%), excluded subjects who had major protocol violations and were judged to have a significant impact on the results. All protocol deviations causing the exclusion of subjects from the compliant protocol set will be described in detail in the Statistical Analysis Plan (SAP) and completed prior to data lock.

5.3 5 Statistical analysis plan

Data description of statistical analysis, analysis method of primary / secondary indicators / safety indicators, statistical school positive method, control of bias, stratification / subgroup / sensitivity analysis, etc

Demographic, and other baseline characteristics

Based on the analysis of FAS set, the demographic data, medical history, vital signs and other baseline data were statistically described, where the measurement data (age, BMI, XX, etc.) gave mean, SD, minimum, maximum, median, and gave frequency and corresponding percentage for count data (gender, XXX, etc.).

Analysis of efficacy indicators

(1) Main efficacy indicators

Point estimates for the main evaluation index (PFS) and estimated two-sided 95% confidence intervals using the Clopper–Pearson exact probability method. If the lower limit of the 97.5% confidence interval is greater than the proportion of 24 months, the treatment group was considered better effective than the historical control.

We obtained the analysis model:

$$Y = b_0 + b_1 \cdot X_1 + b_2 \cdot X_2 + b_3 \cdot X_3 + \epsilon$$

In this equation, the X_i Represents the extent of tumor resection,

X_2 Represents the solid tumor size, X_3 Indicates the medication dose. b_0 Is the intercept, b_1 , b_2 , b_3 Is the regression coefficient of each factor, and the ϵ is the error term.

(2) Secondary efficacy indicators: analysis using FAS and PPS analysis sets. For survival measures, the digit survival time and its two-sided 95% confidence intervals were calculated. For the rate of each index, point estimates were performed and two-sided 95% confidence intervals were estimated using the Clopper-Pearson exact probability method. For the continuity index, the mean and two-sided 95% confidence intervals were calculated based on the normal distribution method, otherwise, the median and two-sided 95% confidence intervals were calculated based on the percentile method.

Safety index analysis

The SS set describes the incidence of adverse events / serious adverse events and adverse reactions, and lists the details of each adverse event in each subject, including the type and severity of adverse events. Safety and evaluation of laboratory indicators, vital signs, electrocardiogram and other safety related indicators, compare and evaluate the changes before and after treatment, and give statistical description of clinical evaluation (normal, abnormal without clinical significance, abnormal with clinical significance, not checked) before and after treatment.

Principles of handling of missing / deleted / lost to follow-up data

Main index analysis adopts LOCF (last observation carried forward) method, that is, the main index data is not observed at the last time; the secondary indicators and safety indicators are not filled.

6. Research intervention*

6.1 Study intervention content (description of intervention content, implementation steps, dose and route of intervention drug, frequency of intervention, product of test group and control group, etc.)

All patients received oral selmetinib hydrosulphate capsules (20–50mg bid) daily for 30 days for 6 cycles, based on individualized patient body surface area (BSA).

6.2 Preparation / handling / storage / responsibilities (drug versus control article allocation plan when intervention should be specified)

The use of drugs must be recorded in the patient's medical record and in the corresponding location of the CRF. After the enrollment of the subjects and at the 1 and 2 months of follow-up, the executive nurse shall receive the corresponding number of drugs at the drug administrator, and the remaining drugs and boxes shall be returned to the drug administrator. If the drug is found or damaged during the preparation process, this box of drugs should not be used, the damaged drugs shall be treated as empty bottles, and other undamaged drugs shall be returned to the drug administrator together with the packaging box. The study center shall be responsible for the management of test drugs, including receiving, distribution, counting and recovery. The investigator shall ensure that the test drug is stored in a safe, independent and locked place at the study site and the storage conditions shall meet the storage requirements of the test drug. No one can be contacted without the consent of the investigator. Empty boxes shall be stored and managed as the test drug.

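### The 17 subjects sized for 80% power give 68.5% under the protocol's own exact Clopper-Pearson success rule

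*Protocol*

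**What the plan says.** Section 5.5.1 of the Protocol gives the design inputs: "The study parameters were set: $\alpha = 0.025$ (unilateral), Power=80"%, a 24-month PFS rate of 20%, and a rate above 50% in the treated patients. The result is "17 cases were calculated using PASS 15.0 software, considering 10% shedding rate, 19 subjects should be included". The PASS procedure is not named. The same section opens by saying "The estimated sample size was based on the objective response rate", although every rate it then uses is a 24-month PFS rate.

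The section on data analysis sets repeats the error level for the primary analysis: "the main indicators use one-sided test, control the first class error α is 0.025".

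Under Analysis of efficacy indicators, (1) Main efficacy indicators, the method is fixed: "Point estimates for the main evaluation index (PFS) and estimated two-sided 95% confidence intervals using the Clopper–Pearson exact probability method". The success rule follows: "If the lower limit of the 97.5% confidence interval is greater than the proportion of 24 months", the treatment is judged better than the historical control. No numerical comparison value is given there.

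For missing data the Protocol states: "Main index analysis adopts LOCF (last observation carried forward) method".

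**The concern.** The sample size and the success rule are both fixed in the Protocol, so they can be checked against each other. An exact binomial limit is more demanding than a normal approximation, and at fewer than 20 subjects a difference of one required success moves power by many points. If 17 came from an approximate formula while success is judged by the exact limit, the 80% does not describe the planned test.

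This is a single-arm trial with one primary decision. At the number for which 80% power is claimed, the chance of missing a true 24-month rate of 50% would be 31.5% instead of 20%. Readers of the Protocol, including an ethics committee, would be relying on a power that the design does not have.

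**Working it through.** **Inputs.** From section 5.5.1: one-sided alpha 0.025, power 80%, p0 = 0.20, p1 = 0.50, 17 evaluable, 10% loss, 19 enrolled. From Main efficacy indicators: Clopper-Pearson lower limit, success if it exceeds the historical 24-month proportion. Two readings are needed. The 20% is taken as the null and the comparison value, because it is the only comparator rate given. The alternative is taken at 50%, the value that reproduces 17.

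**Step 1: reproduce the 17.** One-sample proportion, normal approximation, no continuity correction:

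n = [(1.960 × √(0.2 × 0.8) + 0.8416 × √(0.5 × 0.5)) / 0.3]² = [(0.7840 + 0.4208) / 0.3]² = 16.13, rounded up to 17.

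17 / 0.9 = 18.9, rounded up to 19.

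Other common formulas give different sizes: null variance only 13.95, alternative variance only 21.80, continuity-corrected 19.32, arcsine 18.95. A logit-scale formula using the alternative's variance (16.34) also rounds to 17, so the method is inferred from the match. The steps below do not depend on it.

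**Step 2: the exact rule at 17.** The lower end of a two-sided 95% Clopper-Pearson interval, which is the one-sided 97.5% limit, is the 0.025 quantile of Beta(x, n − x + 1).

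- 7/17: 18.4%, below 20%, fails.
- 8/17: 23.0%, passes.

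Success therefore needs at least 8 of 17.

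- Type I error: P(X ≥ 8 | 17, 0.2) = 0.0109.
- Power: P(X ≥ 8 | 17, 0.5) = 0.6855.

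**Step 3: could another cut-off at 17 deliver both properties?** A cut-off of 7 passes the uncorrected z-test: z = (7/17 − 0.2) / √(0.16/17) = 2.18. Its power is P(X ≥ 7 | 17, 0.5) = 0.8338, but its type I error is P(X ≥ 7 | 17, 0.2) = 0.0377, above 0.025. Raising the cut-off from 7 to 8 restores alpha and loses the power. No cut-off at 17 gives both.

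**Step 4: 17 to 19 subjects with observed 24-month status, one-sided 97.5% limit.**

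| n | lower limit at 7 | lower limit at 8 | cut-off | alpha at 20% | power at 50% |
|---|---|---|---|---|---|
| 17 | 18.4% | 23.0% | 8 | 1.1% | 68.5% |
| 18 | 17.3% | 21.5% | 8 | 1.6% | 76.0% |
| 19 | 16.3% | 20.3% | 8 | 2.3% | 82.0% |

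For 80% power with a cut-off of 8, the true rate would have to be about 54.3% at n = 17 or 51.6% at n = 18.

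**Step 5: LOCF, as an illustration.** Assume each dropout was last seen progression-free and is counted as a success, with all 19 analysed and a cut-off of 8.

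- One dropout: alpha P(X ≥ 7 | 18, 0.2) = 5.1%, power P(X ≥ 7 | 18, 0.5) = 88.1%.
- Two dropouts: alpha P(X ≥ 6 | 17, 0.2) = 10.6%, power P(X ≥ 6 | 17, 0.5) = 92.8%.

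If the same dropouts count as failures, power is 76.0% and 68.5%.

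**The case against.** **All 19 may be analysed.** The Protocol applies LOCF to the primary index, the full analysis set keeps every treated subject with an efficacy assessment, and no analysis set is named for the primary index. The denominator may then be 19, with power of 82.0% or more. This stands as a condition: the shortfall after 10% loss holds if lost subjects are excluded or counted as failures. It does not rescue the design. The power gained by counting dropouts as successes comes with a type I error of 5.1% or 10.6%, against a stated 2.5%.

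**The limit is ambiguous.** The Protocol names a two-sided 95% interval and then a 97.5% interval. If the latter is two-sided, 8/18 and 8/19 have lower limits of 19.1% and 18.0% and fail. The cut-off becomes 9 and power falls to 59.3% and 67.6%. So the figures for 18 and 19 depend on the one-sided reading, which is the one that agrees with the stated alpha. The result at 17 does not: 8/17 is needed either way.

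**The alternative is above 50%, and 20% is not labelled as the null.** Both are readings. At a true rate of 55%, power at 17 is 81.7%, so the 11.5-point gap belongs to 50%. But 50% is the only alternative value the Protocol gives, and it reproduces the 17.

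**The response-rate wording is a separate defect.** Agreed. It contradicts the listed parameters but changes no number here.

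**Conclusion.** The concern holds. With 17 subjects, the exact rule needs 8 successes and gives 68.5% power at a true 24-month rate of 50%, not 80%. The 17 is not an arithmetic slip. It fits an approximate method that does not match the planned analysis. Enrolling 19 reaches 82.0% only if all 19 have observed 24-month status. The loss of about two that the Protocol itself allows for brings power back to 68.5% when those subjects are excluded or counted as failures.

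This rests on 20% as the comparison value, 50% as the alternative and the 24-month rate analysed as a binomial proportion. The figures for 18 and 19 also rest on the one-sided 97.5% limit. The point should be fixed, and confidence is high.

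**What to change.** 1. In section 5.5.1, replace the claim of 80% power for 17 with text such as: *Under the exact Clopper-Pearson rule (one-sided 97.5% lower limit above 20%), success requires at least 8 progression-free subjects; power at a true rate of 50% is 68.5%, 76.0% and 82.0% with 17, 18 and 19 subjects whose 24-month status is observed.*
2. Under Main efficacy indicators, define the decision limit as the one-sided 97.5% Clopper-Pearson lower limit and compare it with 20%. This is the lower end of the two-sided 95% interval already named there and agrees with the one-sided alpha of 0.025.
3. In section 5.5.1, name the 2-year PFS rate, not the objective response rate, as the sizing basis.
4. Do not claim control of type I error where LOCF fills in the primary index. The powers in item 1 describe observed status only.

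The cost is Protocol wording and a less favourable stated power; enrolment is unchanged. Restoring 80% after 10% loss is a separate enrolment decision. For orientation, 19 is the smallest evaluable number with exact power of at least 80% (19/0.9 = 21.1, so 22 enrolled), but exact power is not monotone: 20 evaluable gives 74.8% and 23 gives 79.8%. It stays above 80% for every number checked from 24 to 31 (24/0.9 = 26.7, so 27 enrolled).
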